## Appendix B. Adaptive Reserve and Change Process Capability Questionnaires

### B.1 Practice Structure

1. Approximately how often do the clinicians and staff at your practice site **hold meetings** to discuss the practice site's performance on:

*Check (✓) one for each of the following listed meeting topics:*

*(Response options: Never, Annually, Quarterly, Monthly, More often than monthly)*

- a. Overall pediatric quality of care?
- b. Patient satisfaction ratings?
- c. Productivity?
- d. Utilization or costs of care?
- e. Clinician or staff satisfaction?

2. Does your practice monitor the clinician(s) personal performance on ...

*(Response options: No, Yes, Don't know)*

- a. Overall pediatric quality of care
- b. Patient satisfaction ratings? (e.g., patient experience surveys)
- c. Productivity? (e.g., patient volume, procedure volume)
- d. Utilization or costs of care?

3. Does your practice monitor staff members' personal performance on...

*(Response options: No, Yes, Don't know)*

- a. Overall pediatric quality of care
- b. Patient satisfaction ratings? (e.g., patient experience surveys)
- c. Productivity? (e.g., patient volume, procedure volume)
- d. Utilization or costs of care?

4. Do the clinicians at your practice site use planned communications (e.g., letters, phone calls, text messages) to contact patients who are due for preventive care visits

*(Response options: No, Yes, Don't know)*

5. Does your practice site have:

*Check (✓) one for each of the following listed items:*

*(Response options: No, Yes, Don't know)*

- a. Agreements with community service agencies (e.g., health departments) to enhance services for any of your patients?
- b. A referral system for linking your patients to tobacco cessation programs

6. During a typical day in clinic, how often do providers use a computer or other electronic device (e.g., tablet, smart phone) to look up information about the patients they are seeing?

*Check (✓) one:*

- a. Never
- b. Rarely
- c. Sometimes
- d. Usually
- e. Always

7. Does your practice have an electronic medical record?
  - a. No
  - b. Yes
  
8. Does your site utilize an electronic medical record (EMR or electronic health record (EHR)?
  - a. Yes
  - b. No
  
9. If YES, please select the vendor of your practice's EHR:
  - a. Allscripts
  - b. CERNER
  - c. eClinicalWorks
  - d. eMD
  - e. EPIC
  - f. GE Healthcare Centricity
  - g. McKesson
  - h. NextGen
  - i. Practice Partner
  - j. Care360
  - k. Practice Fusion
  - l. SOAPware
  - m. Don't Know
  - n. Other, please specify: \_\_\_\_\_

## **B.2 Change Process Capability Questionnaire (CPCQ)**

1. How would you describe the current status of and attitudes toward quality improvement in your pediatric practice?  
 (*Response options: strongly disagree, somewhat disagree, neither agree or disagree, strongly agree, N/A*)
  - a. We have greatly improved the quality of care in the past year
  - b. We choose new processes of care that are more advantageous than the old to everyone involved (patients, clinicians, and our entire group/clinic)
  - c. Our resources (personnel, time, financial) are too tightly limited to improve care quality now
  - d. The clinicians and staff in our practice have a shared vision about how we define quality of dental care
  - e. The clinicians in our practice adhere to practice policies
  - f. Our practice has well-developed administrative structures and processes in place to create change
  - g. Our practice is undergoing considerable stress as the result of internal changes
  - h. The working environment in our practice is collaborative and cohesive, with a shared purpose, cooperation, and willingness to contribute to the common good
  - i. Our practice has a well-defined quality improvement process for designing and introducing changes in the quality of care
  
2. Our pediatric practice has used the following strategies to implement improved care quality...  
 (*Response options: strongly disagree, somewhat disagree, neither agree or disagree, strongly agree, N/A*)
  - a. Providing information and skills-training
  - b. Use of opinion leaders, role modeling, or other vehicles to encourage support for changes
  - c. Changing or creating systems in the practice that make it easier to provide high quality care

- d. Removal or reduction of barriers to better quality of care
- e. Organizing people into teams focused on accomplishing the change process for improved care
- f. Providing to those who are charged with implementing improved care the power and authority to make desired changes
- g. Using periodic measurement of health care quality to determine the effects of a new intervention
- h. Developing reports documenting the measurements of individual or practice performance
- i. Setting goals and benchmarking rates of performance quality at least yearly
- j. Customizing the implementation of any care changes to the practice site
- k. Deliberately designing care improvements so as to make dentist participation less work than before
- l. Deliberately designing care improvements to make the care process more beneficial to the patient

## Appendix C. Youth Tobacco and Nicotine Product Questionnaire (Y-TNPQ)

### Section 1. Screening Questions:

1. Have you ever used any of the following tobacco products, even one or two times? Check all that apply.
  - a. Cigarettes
  - b. E-cigarettes, such as Blu or Smoking Everywhere
  - c. Cigars, cigarillos, or filtered cigars
  - d. Hookah, shisha, or waterpipe
  - e. Smokeless tobacco, such as snus, pouches, snuff, dip, or chewing tobacco
  - f. I have never used tobacco products

- If Q1=a **[go to Q2]**
- If Q1=b **[go to Q3]**
- If Q1=c **[go to Q4]**
- If Q1=d **[go to Q5]**
- If Q1=e **[go to Q6]**
- If Q1= f **then never established tobacco use, [assess susceptibility using the items S1-S3]**

2. Do you currently use any tobacco products such as cigarettes, e-cigarettes, cigars, cigarillos or filtered cigars, hookah, shisha or waterpipe, snus pouches, snuff, dip, or chewing tobacco every day, some days, or not at all?
  - a. Everyday
  - b. Some days
  - c. Not at all

S1. Do you think you might try a cigarette or other tobacco product?

- a. Definitely yes
- b. Probably yes
- c. Probably not
- d. Definitely not

S2. If one of your best friends were to offer you a cigarette or other tobacco product, would you use it?

- a. Definitely yes
- b. Probably yes
- c. Probably not
- d. Definitely not

S3. Do you think you might be smoking cigarettes or using tobacco 1 year from now?

- a. Definitely yes
- b. Probably yes
- c. Probably not
- d. Definitely not

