### 6.2.2 Sample

In Florida, only 4.3 percent of children ages 11 to 17 are current cigarette smokers. However, e-cigarette use is increasing from 5 percent of Florida high school students in 2013 to 11 percent in 2014. While the percentage of adolescents at risk to begin smoking is not known, studies have identified maternal smoking, trying tobacco, alcohol or marijuana by 8th grade, and endorsement of sensation seeking behavior as risk factors for tobacco and related product use. Children should be screened for these risks.

We will screen all youth, ages 11 through 17 years, in the practice for current tobacco use and risk behaviors associated with cigarette and nicotine product use with the goal of reaching 20 children per practice who are current tobacco users who could receive at least one or more of Steps 3 through 6 (advise, assess, assist, arrange). To achieve 20 patients per practice who reach the “advise” and “assess” stages, if the practice had the average percentage of children using e-cigarettes, approximately 218 patients would need to be screened. The number screened to reach the “advise” and “assess” stages is based on the e-cigarette use and not the traditional cigarette use.

Intervention practices will be asked to screen patients for tobacco and nicotine product use (using the anticipate and ask components of the 6As) by having youth complete a tobacco and nicotine use screening tool until the practice has identified and completed at least the “advise” and “assess” intervention on 20 tobacco/nicotine users. Parental consent and adolescent assent will be electronically obtained using ResearchActs software. In addition, practices will be asked to implement a short parental screening tool for tobacco use. The parent and child will respond to the surveys separately. After the child completes the survey s/he will be offered a \$5 electronic Amazon gift card.

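### As printed, the youth screening form asks about current use only of those who have tried cigarettes, so e-cigarette and other-product users who never smoked are not asked

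*Combined protocol and SAP*

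**What the plan says.** Section 6.2.2 states the purpose of screening: "We will screen all youth, ages 11 through 17 years, in the practice for current tobacco use and risk behaviors". It assigns the anticipate and ask steps to the youth questionnaire. It gives the screening load per practice as "approximately 218 patients would need to be screened" and says that this number "is based on the e-cigarette use and not the traditional cigarette use". Screening continues until the practice has completed at least advise and assess, as an "intervention on 20 tobacco/nicotine users". After listing risk factors that include maternal smoking, the section adds: "Children should be screened for these risks".

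The questionnaire is the Y-TNPQ in Appendix C. Question 1 asks about ever-use of five product groups and allows several answers. Each answer has its own printed destination. Question 2 is the only question on the youth's own current use: "Do you currently use any tobacco products such as cigarettes, e-cigarettes, cigars, cigarillos or filtered cigars, hookah, shisha or waterpipe", and the list goes on to smokeless products. Never-users answer three susceptibility questions (S1 to S3) and are then sent to Question 7.

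Section 6.2.3 C says that the questionnaire is still to be programmed into ResearchACTS, and that the clinician reviews the answers at the visit.

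**The concern.** Question 2 is written for users of any product, but the routing treats it as a question for cigarette users. A youth who uses e-cigarettes and has never tried a cigarette goes from the ever-use question straight to a question about other people in the home. The clinician then sees an ever-use answer and no current-use answer.

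This matters for Aim 1, which is to develop and deploy this tool. Section 4 says that screening will include e-cigarettes, cigars, chewing tobacco and hookah. The study's own record-review form (Appendix E, item 1) scores whether current use was asked for each of five product groups. The tool asks about current use after only one of the five corresponding ever-use answers. The group most exposed to the gap is the one on which Section 6.2.2 bases its screening number.

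**Working it through.** **1. The printed routes (Appendix C, Section 1).**

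| Answer to Question 1 | Sent to | Content of that question | Own current use asked? |
|---|---|---|---|
| a. Cigarettes | Question 2 | Own current use, all products | Yes |
| b. E-cigarettes | Question 3 | Use by household members | No |
| c. Cigars | Question 4 | Age | No |
| d. Hookah | Question 5 | Sex | No |
| e. Smokeless | Question 6 | Grade | No |
| f. Never used | S1 to S3, then Question 7 | Susceptibility, then Hispanic origin | Not applicable |

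No instruction leads from Questions 3 to 6 back to Question 2.

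**2. Answer patterns.** Five products give 2^5 − 1 = 31 possible patterns of ever-use. Cigarettes appear in 2^4 = 16 of them, and these can reach Question 2. The other 31 − 16 = 15 cannot. Even for the 16, a youth who ticks cigarettes and another product has two or more destinations, and no rule says which applies. These are counts of patterns, not of youth.

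**3. Never-users.** The jump from S3 to Question 7 skips Questions 3 to 6: household use, age, sex and grade. The parent form (Appendix D) covers household use only in part. Items 3 to 5 ask about the responding parent's own use and item 2 about tobacco being available at home. Use by other household members is not asked.

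**4. The plan's screening number.** The rates given are "only 4.3 percent of children ages 11 to 17 are current cigarette smokers" and, for e-cigarettes, a rise "from 5 percent of Florida high school students in 2013 to 11 percent in 2014". Then 20/0.11 = 181.8, or 182, and 20/0.05 = 400. Neither gives 218, which implies 20/218 = 9.17%. Section 6.2.3 C uses about 190, which implies 20/190 = 10.5%. That mismatch is a separate matter, and the routing fault does not depend on it.

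**5. Size.** Let s be the share of current e-cigarette users who have ever tried a cigarette. The documents do not give s. As an illustration, take the plan's implied 20 e-cigarette users among 218 screened. The number not asked about current use is 20 × (1 − s):

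- s = 1: 0
- s = 0.75: 5
- s = 0.5: 10
- s = 0.25: 15
- s = 0: 20

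Anyone who smokes now has tried a cigarette, so s cannot be below the share of e-cigarette users who currently smoke. At 4.3%, 218 × 0.043 = 9.4 youth smoke. If all of them also use e-cigarettes, at most 20 − 9.4 = 10.6 are not asked; if none do, the ceiling is 20.

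The illustration assumes that the implied 9.17% is a current-use rate (Section 6.2.2 says current for cigarettes but not for e-cigarettes), that it holds for ages 11 to 17, and that a youth who ticks cigarettes plus another product goes to Question 2. Users of only cigars, hookah or smokeless tobacco are not counted, because no rates are given.

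**The case against.** The strongest reply is that this is stale numbering in a paper appendix. The destinations for b to e, and the jump to Question 7, would fit a questionnaire with a separate use question for each product at Questions 2 to 6. Appendix B also carries leftovers, with references to dental care in a pediatric survey. The programmed form may already differ. This is a plausible explanation, but nothing in the documents corrects the routing, and Section 6.2.3 C speaks of programming still to come.

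The second reply is that the visit makes up for the gap. Section 6.2.2 allows 2 to 5 minutes of clinician screening and advising for the child and lets nurses or physicians do it. Section 6.2.3 C describes prompts that take the clinician through the 6As. The positive ever-use answer is also on the screen. This limits the harm but does not remove the fault: Section 6.2.2 gives the ask step to the questionnaire, and the prompts depend on what the youth answered.

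A reader might infer more than the documents support:

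- *That accrual will fail.* Practices screen until 20 users complete advise and assess, with no stated cap at 218, and accrual does not count Question 2 answers. Missed users could lengthen screening; a missed target is not shown.
- *That the form finds 20 users only above some value of s.* Users of cigars, hookah or smokeless tobacco who have also tried cigarettes reach Question 2 and would add to the count, so no such threshold follows.
- *That the primary outcome is biased.* It comes from medical records, and no analysis in Section 6.2.5 names the Y-TNPQ. Age and gender are model covariates there, but the plan does not say that they come from this form.
- *That Question 2 leads nowhere.* S1 to S3 are reserved for never-users, so the natural reading is that Question 2 runs on to Question 3.

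**Conclusion.** The point holds for the form as printed. Appendix C contradicts Section 6.2.2: ever-users of other products who never tried a cigarette are not asked about current use. The missing rule for several ticked products and the never-user jump are further faults in the same skip logic; the second is weaker because the parent form gives partial cover.

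The size cannot be fixed from the documents. It runs from no e-cigarette users missed to all those who do not currently smoke, and the figures above are illustrations under stated assumptions. The fault lies in the Aim 1 tool and possibly in the pace of accrual. It should be corrected before the form is used, but it does not undermine the primary analysis. Whether the deployed form shares it cannot be told from the documents.

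**What to change.** Before programming, or by checking the programmed version:

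- route any of answers a to e in Question 1 to Question 2, and from there to Question 3;
- send never-users from S1 to S3 to Question 3;
- have everyone complete Questions 3 to 8;
- delete the separate destinations for b to e and the jump to Question 7.

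One shared route for all ever-users also settles what happens when several products are ticked: all 31 answer patterns then reach Question 2.

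The cost is corrected skip logic in Appendix C and the iPad form, plus a few short questions. If youth now continue in number order from their printed destination, those who tick one product gain: e-cigarettes 1 (Question 2), cigars 2 (Questions 2 and 3), hookah 3 (Questions 2 to 4), smokeless 4 (Questions 2 to 5). Never-users gain 4 (Questions 3 to 6) and cigarette users none. If the programmed form already works this way, only the appendix needs correcting.

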**Upon completion of S1-S3 go to Q7.**

3. Does anyone who lives with you now...?

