**(CHOOSE ALL THAT APPLY)**

- a. Smoke cigarettes
- b. Smoke cigars, cigarillos, or little cigars
- c. Use chewing tobacco, snuff, or dip
- d. Use electronic cigarettes or e-cigarettes
- e. Smoke tobacco from a hookah or waterpipe
- f. Smoke pipes filled with tobacco (not waterpipe)
- g. Use snus
- h. Use dissolvable tobacco products
- i. Smoke bidis (small brown cigarettes wrapped in a leaf)
- j. No one who lives with me now uses any form of tobacco

4. How old are you?

- a. 11 years old
- b. 12 years old
- c. 13 years old
- d. 14 years old
- e. 15 years old
- f. 16 years old
- g. 17 years old

5. What is your sex?

- a. Male
- b. Female
- c. Don't know, or something else

6. What grade are you in?

- a. 5th
- b. 6th
- c. 7th
- d. 8th
- e. 9th
- f. 10th
- g. 11th
- h. 12th
- i. Ungraded or other grade
- j. In college/university

7. Are you Hispanic, Latino/a, or Spanish origin (One or more categories may be selected)?

- a. No, not of Hispanic, Latino/a, or Spanish origin
- b. Yes, Mexican, Mexican American, Chicano, or Chicana
- c. Yes, Puerto Rican
- d. Yes, Cuban
- e. Yes, Another Hispanic, Latino/a, or Spanish origin

8. What race or races do you consider yourself to be?  

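### As printed, the Y-TNPQ skip sends every never-user past household tobacco use, age, sex and grade; the skip targets do not match the item numbers and need correcting

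*Combined protocol and SAP*

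**What the plan says.** Section 6.2.2 (Sample) commits to a broad screen: "We will screen all youth, ages 11 through 17 years, in the practice for current tobacco use and risk behaviors". It names maternal smoking, early trying of tobacco, alcohol or marijuana, and sensation seeking as risk factors, and adds: "Children should be screened for these risks".

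The youth instrument is Appendix C. Its item 1 asks about ever-use of five product types. A youth who ticks the never-used option is to "assess susceptibility using the items S1-S3". The next instruction is "Upon completion of S1-S3 go to Q7".

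The items around that skip are:
- item 3: "Does anyone who lives with you now", followed by a list of tobacco products
- item 4: "How old are you"
- item 5: "What is your sex"
- item 6: school grade
- item 7: "Are you Hispanic, Latino/a, or Spanish origin (One or more categories may be selected"

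Section 6.2.3, part C, says the questionnaire will be programmed into ResearchACTS and that the clinician will review the child's answers at the point of care. Appendix C is therefore the only specification of the routing that the documents give.

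**The concern.** Never-users are the youth who can still start, and household exposure is the only Y-TNPQ item about tobacco use by others in the home. If the software follows the printed rule, the clinician reviewing a never-user's answers sees nothing from the child on that subject. Yet discussion of the parent's tobacco use is one of the primary outcome measures in section 6.2.5, and the follow-up call (Appendix F, item 8) asks whether a clinician asked the youth about use by parents or others in the home.

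Any description of screened youth by questionnaire age, sex, grade or household exposure would also leave out every never-user. Age and sex can probably be recovered from the medical record. A youth's own report of household use cannot be recovered from the questionnaire afterwards.

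**Working it through.** The plan states no figure for this point, so the check is a trace of the printed routing followed by a sizing.

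**Trace.** Inputs are the skip rules under item 1 and after S3, and the item numbers as printed in Appendix C. Assumptions: one product ticked, and the respondent continues in number order after landing. No skip is printed after item 2, and no rule covers a youth who ticks several products.

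| Answer to item 1 | Sent to | Items among 2–6 never reached |
|---|---|---|
| a, cigarettes | 2 | none |
| b, e-cigarettes | 3 | 2 (current use) |
| c, cigars | 4 | 2, 3 (household) |
| d, hookah | 5 | 2, 3, 4 (age) |
| e, smokeless | 6 | 2, 3, 4, 5 (sex) |
| f, never used | S1–S3, then 7 | 2, 3, 4, 5, 6 (grade) |

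Omitting item 2 is appropriate for a never-user. Omitting items 3 to 6 is not explained anywhere.

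**Likely cause (inference).** The five product answers point to five consecutive numbers, 2 to 6, and the never-user branch points to 7. That fits a form with one current-use item per product at 2 to 6 and the first common item at 7. Only one combined current-use item is now printed, and the first common item, household use, now carries number 3. On this reading the never-user branch was meant to arrive at the household item.

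**What never-users still provide.** Item 1 (ever-use), S1–S3 (might try, a friend's offer, use in a year), ethnicity and race. In Appendix D (PBQ), item 2 asks about tobacco availability at home and items 3 to 5 ask about the responding parent's own use in the past 30 days. A second parent or other household member is not covered.

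**Size.** Never-users affected per practice = number completing × proportion who have never used. The documents give no ever-use rate; 70% to 90% never-users is assumed. Section 6.2.3 gives about 190 completers per intervention practice; section 6.2.2 gives about 218 to be screened.

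- 190 × 0.70 = 133; 190 × 0.90 = 171
- 218 × 0.70 = 152.6, about 153; 218 × 0.90 = 196.2, about 196

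Over the two intervention practices, on the 190 figure: 2 × 133 = 266 to 2 × 171 = 342.

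**The case against.** The strongest reply is that this is a numbering slip with no analytic consequence. Section 6.2.5 takes the primary outcome from medical records. The Y-TNPQ is described for intervention practices only, so it could not supply age and gender for both arms of the model. No planned analysis uses youth-reported household exposure. Most of this stands: no planned analysis is shown to be harmed. It does not remove the fault, because a rule followed as written loses data that the clinician was meant to see. Whether the programmed version already differs from the printed one cannot be told from the documents.

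Four stronger readings are tempting and are not supported:

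- *The risk screen is lost in never-users.* It is not. The susceptibility items are asked, item 1 is asked, and the PBQ covers part of the home exposure. Age, sex and grade are not among the risks named in section 6.2.2.
- *The skip explains the absence of alcohol, marijuana and sensation-seeking data.* Appendix C has no such items for any respondent. That is a separate mismatch with section 6.2.2.
- *Household data would come from all ever-users and no one else.* Youth who tick only cigars, hookah or smokeless tobacco also land past item 3. As printed, only those who tick cigarettes or e-cigarettes reach it.
- *Former users should be routed through S1–S3.* Appendix C directs those items to never-users, and asking whether one might try tobacco does not fit someone who already has. Adding that route would be a preference, not a correction.

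It is also fair to say that this shares its probable cause with the product skips that bypass item 2. It still needs its own correction: repairing only those skips would leave the never-user branch pointing to item 7.

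**Conclusion.** The concern holds in a limited form. As printed, all never-users miss household tobacco use, age, sex and grade. The loss that matters is youth-reported household exposure at the point of care, which the PBQ replaces only in part. The size is about 133 to 171 youth per intervention practice on 190 completers, or 153 to 196 on 218, and rests on the assumed 70% to 90% never-use. The routing itself is read directly from Appendix C; stale numbering as the cause, and recovery of age and sex from the record, are inferences. The record-based primary analysis is not shown to be affected. The correction should be made before the tool is used because it is almost free and the household answers cannot be recovered from the questionnaire later.

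**What to change.** In Appendix C, change the instruction after S1–S3 so that it leads to item 3. In the same edit, correct the targets for answers b to e of item 1 so that users of any product reach the current-use item and every respondent reaches items 3 to 8. Test every path in ResearchACTS before use, including youth who tick more than one product.

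Separately, in section 6.2.2, limit the statement on risk screening to what the tools measure: tobacco use, susceptibility, and household and parental use.

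The cost is a handful of skip rules, one sentence in section 6.2.2, a short round of software testing, and four brief extra questions for each never-user.
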